## 1. Background

Primary liver malignancy (primary liver cancer) occurs at the epithelial or mesenchymal tissue of the liver, mainly including hepatocellular carcinoma, intrahepatic cholangiocarcinoma and combined hepatocellular cholangiocarcinoma, in which hepatocellular carcinoma accounts for more than 85%~90%, being the most common malignant tumor in China.

Currently, the incidence of liver cancer is steadily increasing at a rate of 3% per year around the world. The Asia and China have the highest burden of liver cancer, 70% of patients with newly-developed liver cancer is from Asia and 50% from China. Correspondingly, the number of patients died from liver cancer in China also accounts for half of that in the world. Chinese Cancer Center published the latest data about the cancer on Chinese Journal of Oncology in January 2018: In total number of patients with newly-developed malignant tumors in China, the frequency of liver cancer ranks fourth (365,000 cases/year); In total number of patients died from malignant tumors, the frequency of liver cancer ranks second (319,000 cases/year). The risk of liver cancer is especially higher in men older than 40 years old.

The pathogenesis and exact molecular mechanism of primary liver cancer are not yet fully understood. At present, the pathogenesis of primary liver cancer is believed to be a complex process with multiple factors and steps, which is affected by both environment and diet. The data of epidemiology and relevant studies show that infections of hepatitis B virus (HBV) and hepatitis C virus (HCV), aflatoxin, water pollution, alcohol, liver cirrhosis, sex hormones, nitrosamines, trace elements are associated with liver cancer. Secondary liver cancer (metastatic liver cancer) can induce the disease through different pathways, such as blood, lymphatic metastasis, or direct invasion of the liver.

At present, the routine surveillance and screening indicators for the early diagnosis of liver cancer mainly include alpha-fetoprotein (AFP) and liver ultrasound examination (US). Based on domestic and foreign reports and clinical verification, the sensitivity of

AFP in diagnosing liver cancer is about 60%, the false negative rate is 40%, the specificity is about 80%, and the false positive rate is 20%. For these reasons, AFP is no longer a screening indicator in AASLD guideline. For nodules larger than 2 cm, the sensitivity of US is still 84%; but for nodules of 0.5~2 cm in the liver, the sensitivity is only 33%. Therefore, there is an urgent need to find out a new biomarker for auxiliary diagnosis of liver cancer with higher sensitivity and specificity compared with current screening methods.

ctDNA, also known as Cell-free tumor DNA or circulating tumor DNA, circulates freely in the blood of patients with cancer. The analysis and comparison between ctDNA mutation and the site of normal genome by means of invasive approach can provide the useful information for tumor diagnosis, prognosis, and monitoring.

ctDNA generates from necrotic or apoptotic tumor cells, circulating tumor cells, and exosomes secreted by tumor cells. In the body of cancer patients, the number of ctDNA is small, the half life is short, and the size of ctDNA is about 160~180 bp. These fragments can reflect the number of tumor cells and its change. ctDNA is the "identity fingerprint" released by tumor cells into the blood, which is a tumor marker with high sensitivity and specificity . ctDNA is a non-invasive alternative for patients who are not suitable for tumor biopsy, which not only relieves the suffering, but also serves as an alternative to repeated invasive biopsy.

DNA methylation refers to the covalent bonding of a methyl group at the 5' carbon position of cytosine of genomic CpG dinucleotides under the action of DNA methyltransferases. DNA methylation is an important epigenetic mark information and one of the earliest discovered DNA modification pathways. It plays an important role in maintaining normal cell function, genetic imprinting, embryonic development and human tumorigenesis, and is also one of the popular topics of study. Alterations in DNA methylation level and pattern are an important factor in tumorigenesis. In normal cells, the CpG island located in the promoter region of tumor suppressor genes is in a low level or unmethylated state. At this time, tumor suppressor genes are in a normal open state, and the expression of tumor suppressor genes inhibits tumorigenesis. In tumor cells, the CpG

island in this region is highly methylated, the chromatin conformation is altered, and tumor suppressor gene expression is turned off, resulting in cell entry into the cell cycle, loss of apoptosis, defective DNA repair, dysfunction of vessel growth and cellular adhesion, eventually leading to tumorigenesis. DNA methylation is an ideal biomarker and evaluation indicator for prognosis and early diagnosis of tumors, and it is of great significance for tumor screening, risk assessment, early diagnosis, staging, prognosis judgment, treatment and monitoring.

DNA methylation changes are an early event in the tumorigenesis of hepatic cancer, including increased methylation of tumor suppressor genes or decreased methylation of proto-oncogenes, and this change precedes mutation of driver genes. Therefore, changes in methylation patterns are considered to be the first detectable indicator closely related to tumorigenesis, providing a screening window for early diagnosis of liver cancer. By analyzing the ctDNA methylation model in a large number of patients with liver cancer and normal individuals, we finally screened out 6 liver cancer ctDNA-specific gene methylation sites, and established a comprehensive methylation diagnostic model with high-sensitivity and specificity. On this basis, the human 6 gene methylation test kit (PCR-fluorescent probe method), which is a novel blood-based DNA methylation assay, was developed.

## **2. Objective of Clinical Trial**

- 1) Test performance evaluation
- 2) Diagnostic performance evaluation

## **3. Overall Design of Clinical Trial**

### **3.1 Selection of clinical trial centers**

The representative centers are selected to conduct this clinical trial, based on the consideration of the characteristics of the product, the intended use, the demographics, the epidemiologic background, the features of pathogenic microorganism, the study population, the clinical conditions (expected use environment and users).

## 3.2 Test performance evaluation

### 3.2.1 Test performance evaluation method

Following the principle of concurrent blinding, the blood samples are collected from the non-HCC patients and patients with liver cancer who had been diagnosed according to the clinical diagnostic criteria for primary liver cancer. The clinical diagnosis of primary liver cancer is determined in accordance with the clinical diagnostic criteria in Guidelines for diagnosis and treatment of primary liver cancer (2019 Edition) set by the National Health Commission. The enrolled subjects are coded. The selected samples are tested with test reagent and the control method high-throughput human methylation sequencing (NGS sequencing method), the test results are compared.

### 3.2.2 Determination of the sample size for test performance evaluation

According to the pre-clinical independent cohort verification results of 6 liver cancer-specific methylation sites that were screened out, the number of positive samples should be not less than 78; the number of negative samples should be not less than 238; the samples available in this study should be not less than 316 cases.

Considering that the mutation rate of some genes is extremely low (AK055957, DAB2IP, TBX15, GRASP, PPFIA1, PSD4), the subjects should be enrolled sequentially, and at least one positive case should be screened out in each type of gene mutation. If the requirements are not met, more subjects should be enrolled for testing. It should be ensured that all samples are traceable.

### 3.2.3 Inclusion Criteria

- 1) Confirmed primary hepatocellular carcinoma or confirmed non-HCC;
- 2) I or my legal representative can read, understand and sign the informed consent;
- 3) Agree to provide blood samples and have good clinical compliance;
- 4) The basic clinical information is complete, including: the patient's unique traceability number (ID number/outpatient clinic number/medical insurance card number), age, gender, imaging and/or pathological diagnosis results (for patients with primary liver

cancer), imaging examination confirmed non-identical Liver cancer (non-HCC patients).

### 3.2.4 Exclusion Criteria

- 1) pregnant women;
- 2) Have received an organ transplant;
- 3) Non-HCC patients diagnosed with other tumors;
- 4) Patients with primary hepatocellular carcinoma combined with other tumors;
- 5) The investigator judges that they are not eligible for inclusion.

## 3.3 Diagnostic performance evaluation

### 3.3.1 Diagnostic performance evaluation method

According to the clinical diagnosis results of typical primary liver cancer imaging, the enrolled subjects at a high risk of primary liver cancer should undergo alpha-fetoprotein (AFP) test, liver ultrasound examination (US), test with test reagent and dynamic contrast-enhanced MRI examination, and the sensitivity and specificity of the test reagent should be calculated. AFP will be tested by the conventional method of each center and the method specified by the sponsor.

According to the clinical diagnostic criteria in Guidelines for diagnosis and treatment of primary liver cancer (2019 Edition) set by the National Health Commission: The clinical diagnosis of liver cancer can be made, when a nodule with a diameter  $\leq 2$  cm is found, and minimum 2 examination results in dynamic contrast-enhanced MRI, dynamic contrast-enhanced CT, ultrasound examination and hepatocyte-specific contrast agent Gd-EOB-DTPA contrast MRI show significant brightness during arterial phase, lower brightness of lesion than liver parenchyma during portal venous phase and equilibrium phase (The concentration of the contrast is significantly higher than that of the normal hepatic tumor tissue during arterial phase in a very short period, then decreases during portal venous phase. It's a typical characteristic of liver cancer); The clinical diagnosis of liver cancer can be made, when a nodule with a diameter  $> 2$  cm is found. Therefore, for subjects with typical imaging manifestations of liver cancer but the diameter of

intrahepatic nodule  $\leq 2$  cm, an additional imaging examination will be performed to confirm the diagnosis.

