### 3.3.5 Judgment criteria for negative and positive result of test reagent

The test results of the test reagent are judged according to the positive value in the instructions for use:

When the HCCscan value is greater than 58, the sample is judged to be positive; when the HCCscan value is less than or equal to 58, the sample is judged to be negative.

For the examinations of "US+AFP", the negative result and positive result are determined according to the following criteria:

1) The results of "US+AFP" is positive if one of the following situations is met:

(1) Serum AFP  $> 400$  ng/mL, regardless of whether any nodule is detected by ultrasound examination;

(2) A nodule  $\geq 2$  cm is detected by ultrasound examination, regardless of AFP serum concentration;

(3) A nodule  $\geq 1$  cm but  $< 2$  cm is detected by ultrasound examination, and serum AFP  $\geq 200$  ng/mL

2) Results that do not meet the above criteria are recorded as "US+AFP" negative.

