### 3.7.4 Statistical evaluation of diagnostic performance

Table 2 Comparison of statistical results between the test reagent and clinical diagnostic standards

Test product	Clinical diagnostic criteria		Total
	Positive	Negative	
Positive	A (true positive)	B (false positive)	A+B

Negative	C (false negative)	D (true negative)	C+D
Total	A+C	B+D	A+B+C+D

The calculation formula of the sensitivity is as follows:

$$\text{Sensitivity} = A/(A+C) \times 100\%$$

$$\text{Specificity} = D/(B+D) \times 100\%$$

$$\text{Overall percent agreement} = (A+D)/(A+B+C+D) \times 100\%$$

$$\text{Positive predictive value (PPV)} = A/(A+B) \times 100\%$$

$$\text{Negative predictive value (NPV)} = D/(C+D) \times 100\%$$

The calculation formula of 95% confidence interval:  $p \pm 1.96 \times [p(1-p)/n]^{1/2}$  (where p is sensitivity, specificity, positive predictive value, negative predictive value, total percent agreement, n is the sample size. If  $p > 0.9$ , use Wilson score method for correction.)

At the same time, compare the diagnostic performance of test reagent + AFP, test reagent + AFP + US, AFP + US to the clinical diagnostic criteria.

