### 3.7.5 Comparison of sensitivity across different test methods for screening liver cancer

Make statistical tests on the sensitivity superiority of test reagent + AFP to conventional method (AFP+US) for screening liver cancer, the sensitivity superiority of test reagent + AFP + US to conventional method for screening liver cancer, the sensitivity non-inferiority of test reagent + AFP + US to conventional method for screening liver cancer, the sensitivity non-inferiority of test reagent + AFP + US to conventional method for screening liver cancer.

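### Protocol 3.3.1 gives no imaging condition for nodules over 2 cm, against its own typical-imaging sentences, so Table 2 lacks one clear reference-positive definition; a lesser point is that unblinding in 3.5.3 need not wait for the final diagnosis

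*Protocol*

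**What the plan says.** Protocol 3.3.1 opens with "According to the clinical diagnosis results of typical primary liver cancer imaging" and has every high-risk subject undergo AFP, ultrasound, the reagent and dynamic contrast-enhanced MRI. It then sets out criteria taken from a cited 2019 national guideline:

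- Nodule of 2 cm or less: arterial-phase brightness, then lower brightness than the parenchyma in the later phases, on at least two of the listed examinations.
- Larger nodule: "The clinical diagnosis of liver cancer can be made, when a nodule with a diameter $> 2$ cm is found". No pattern, modality or number of examinations is given.

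The section closes with the consequence: "for subjects with typical imaging manifestations of liver cancer but the diameter of" the nodule no more than 2 cm, "an additional imaging examination will be performed to confirm the diagnosis".

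These criteria supply the columns of Table 2 in 3.7.4, titled "Comparison of statistical results between the test reagent and clinical diagnostic standards", which does not restate them. Under 3.3.5, US+AFP is positive when a nodule of at least 2 "cm is detected by ultrasound examination, regardless of AFP serum concentration". Section 3.7.5 plans to test "the sensitivity superiority of test reagent + AFP to conventional method (AFP+US) for screening liver cancer".

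On blinding, 3.5.3 unblinds once samples have been tested with the reagent and the control method. Section 3.5.2 provides coded tubes and a mapping table kept by separate personnel. Section 3.9 keeps the operator and the evaluator of the test unaware of the diagnosis, and asks that reagent testing and the reference judgment be simultaneous.

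**The concern.** Section 3.3.1 is the only place where the protocol spells out who counts as having liver cancer in the diagnostic part, and sites classify subjects from it. If a site applied the over-2-cm clause as worded, a benign nodule above that size would enter Table 2 as a cancer. The error would be tied to the comparator, because a nodule that ultrasound measures at 2 cm or more is US+AFP positive by definition. It would be scored as a US+AFP true positive and, unless the reagent happened to be positive, as a reagent false negative. An analysis plan could not easily repair reference diagnoses that sites had made on different rules.

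The lesser issue runs the other way. If the reagent result is known while a small nodule is awaiting its added scan, it could influence whether the diagnosis is confirmed, and that would favour the reagent.

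**Working it through.** **Reading the over-2-cm clause.** The opening sentence of 3.3.1 rests the diagnosis on typical imaging. The closing sentence starts from subjects who already have typical imaging and uses size only to decide whether a further examination is needed. Both fit a rule that requires typical imaging at either size. The clause between them does not state that condition. The passages therefore conflict, and the surrounding text points to an omission.

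**Size: illustration only.** The plan states no figure to reproduce. Inputs:

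- C, true cancers: 90, 135 or 225, that is 2, 3 or 5% of the 4500 in 3.3.2 (percentages assumed).
- Reagent sensitivity 0.80 and true gain of reagent + AFP over AFP+US 0.20 (assumed).
- B, benign nodules over 2 cm counted as reference-positive: 0, 5 or 10 (assumed).
- q, share of these positive on the reagent or on reagent + AFP: 0.10 to 0.30 (assumed).
- u, share seen by ultrasound: 0.84. The Background says "For nodules larger than 2 cm, the sensitivity of US is still 84" percent; carrying this to benign nodules is an assumption.

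Apparent gain = (0.20·C + B·(q − u)) / (C + B). This is a weighted average of 0.20 and q − u, so it falls whenever q − u is below 0.20. With q at most 0.30, any u above 0.10 is enough, so the direction does not depend on the 84%.

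- B = 0: 20 points, no distortion.
- B = 5 (0.11% of 4500): from (18 − 3.7)/95 = 15.1 to (45 − 2.7)/230 = 18.4 points.
- B = 10 (0.22%): from (18 − 7.4)/100 = 10.6 to (45 − 5.4)/235 = 16.9 points.
- B = 5 with u = 0.33 (the Background figure for 0.5 to 2 cm, used only as a low value): from (18 − 1.15)/95 = 17.7 to (45 − 0.15)/230 = 19.5 points.

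Reagent sensitivity = (0.80·C + q·B)/(C + B):

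- B = 5: 72.5/95 = 76.3% to 181.5/230 = 78.9%.
- B = 10: 73/100 = 73.0% to 183/235 = 77.9%.

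The gain vanishes at B = 0.20·C/(u − q), from 18/0.74 = 24.3 to 45/0.54 = 83.3 nodules, or 0.54 to 1.85% of 4500.

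For reagent + AFP + US against AFP+US, with any positive component counting (assumed), the gain is (0.20·C + 0.16·q·B)/(C + B). For B = 5 or 10 it runs from 18.16/100 = 18.2 to 45.24/230 = 19.7 points, so it is barely affected.

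**Reading the unblinding trigger.** Section 3.2.1 names the control method as NGS sequencing, in the test performance part. Section 3.4.1 draws two tubes there for reagent and control method, but one tube in the diagnostic part. Table 1 compares with a control method; Table 2 compares with clinical diagnostic criteria. Section 3.9 lists the clinical reference standard and comparative reagents as different things. In the diagnostic part the trigger therefore reduces to completion of reagent testing. The protection in 3.9 runs from diagnosis to test operator. No passage states the reverse, and simultaneous conduct does not say which result is recorded first when an added scan is pending.

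For scale, suppose k reagent-negative cancers with small nodules are left unconfirmed. Sensitivity then reads 0.80·C/(C − k):

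- k = 1: 72/89 = 80.9% to 180/224 = 80.4%.
- k = 3: 72/87 = 82.8% to 180/222 = 81.1%.

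**The case against.** The strongest reply on the main point is that the paragraph resolves itself. It relies on a named guideline, requires contrast MRI of everyone, and closes with a sentence that makes sense only if typical imaging is needed at both sizes. That largely stands: typical imaging is the likely intent, and then no result changes. It does not remove the conflict, because the one clause that states the over-2-cm rule omits the condition.

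The figures are also open to challenge. Every rate is assumed, and the exclusion of other diagnosed tumours in 3.3.4 could remove some benign lesions before they count. This stands too. The result is set by the assumed B: with 180 cancers and 43.2 such nodules (1% of the 4320 others), q = 0.10 and u = 0.84, the gain would read (36 − 31.97)/223.2 = 1.8 points.

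On unblinding, 3.5.3 can be read as one study-level step after all testing, which would make early exposure less likely. It does not say that results are released subject by subject. The storage limits in 3.4.3 are maxima and prove no schedule. Even a study-level step is triggered by testing, though, and not by completion of the diagnoses.

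A reader might infer that the protocol means to call every nodule over 2 cm a cancer, that the ambiguity could manufacture a superiority result, or that clinicians are meant to diagnose with the reagent result in hand. The documents support none of these. The surrounding sentences contradict the first, the bias on the literal reading runs against the reagent, and exposure of the diagnosing clinicians is possible but nowhere planned.

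**Conclusion.** The point holds as a conflict of wording in the reference standard, with a second and smaller gap in the unblinding trigger.

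If typical imaging is required at both sizes, the first has no effect. If a site follows the clause literally, reagent sensitivity is understated and the reagent + AFP comparison is biased against the reagent, so the risk is a missed superiority result and not a false one. The amount cannot be derived from the documents; the figures above show only that a handful of subjects could matter if cancers are few.

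The unblinding gap would act in the reagent's favour. Sections 3.5.2 and 3.9 reduce that risk but do not close it, notably for nodules up to 2 cm whose added scan is outstanding.

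**What to change.** In 3.3.1, reconcile the over-2-cm clause with the opening and closing sentences, so that Table 2 rests on one reference-positive definition that states its condition for both size classes. What that clinical condition should be is for the sponsor to settle.

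In 3.5.3, state that in the diagnostic part reagent results are unblinded only after the final clinical diagnosis, including any added imaging, has been recorded without knowledge of the reagent result.

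Both are wording changes. The MRI and the added scan are already planned, so no procedure is added. The cost is a short delay in releasing some reagent results, mainly where an added scan is awaited.

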### 3.3.3 Inclusion Criteria

- 1) Have high risk factors for liver cancer such as HBV and/or HCV infection, alcoholic liver disease, non-alcoholic steatohepatitis, long-term consumption of food contaminated with aflatoxin, liver cirrhosis caused by various other reasons, and family history of liver cancer Wait;
- 2) I or my legal representative can read, understand and sign the informed consent;
- 3) Agree to provide blood samples, be able to receive imaging examinations and have good clinical compliance;
- 4) The complete clinical basic information includes: the patient's unique traceability number (ID number/outpatient clinic number/medical insurance card number), age, gender, etc.

### 3.3.4 Exclusion Criteria

- 1) pregnant women;
- 2) Have received an organ transplant;
- 3) Diagnosed with other tumors;
- 4) The investigators judged that they were not eligible for inclusion.

### 3.3.5 Judgment criteria for negative and positive result of test reagent

The test results of the test reagent are judged according to the positive value in the instructions for use:

When the HCCscan value is greater than 58, the sample is judged to be positive; when the HCCscan value is less than or equal to 58, the sample is judged to be negative.

For the examinations of "US+AFP", the negative result and positive result are determined according to the following criteria:

1) The results of "US+AFP" is positive if one of the following situations is met:

(1) Serum AFP  $> 400$  ng/mL, regardless of whether any nodule is detected by ultrasound examination;

(2) A nodule  $\geq 2$  cm is detected by ultrasound examination, regardless of AFP serum concentration;

(3) A nodule  $\geq 1$  cm but  $< 2$  cm is detected by ultrasound examination, and serum AFP  $\geq 200$  ng/mL

2) Results that do not meet the above criteria are recorded as "US+AFP" negative.

